6.3 Secondary Objectives

1. To describe **at COVID-19 diagnosis date and at treatment index date** the demographic, health and clinical patient characteristics. The following variables will be described:
 - demographics
 - comorbidities (number and type)
 - symptoms (number and type) preceding and/or on the date of diagnosis the diagnosis if captured time from onset of COVID-19 illness symptoms to confirmed diagnosis date.

Some of these characteristics will be stratified by setting, glucocorticoid exposure type (naive, prevalent) and subgroups of special interest. (e.g., chronic cardiac and pulmonary disease, diabetes, renal insufficiency, see Section 7.2.4 Subgroups).

2. To quantify the crude and adjusted (selected confounders tbc) incidence rates and time to onset of adverse events of interest (e.g., infections, hyperglycaemia, hypertension, GI bleeding, composite of cardiovascular events) within **30 and 90 days post treatment index date**, in **various treatment groups**, stratified by setting, glucocorticoid exposure type (naive, prevalent) and subgroups of special interest.

3. To quantify the crude and adjusted incidence rates of mortality and other disease outcomes within **30 and 90 days post treatment index date**, in **various treatment groups**, stratified by setting, glucocorticoid exposure type (naive, prevalent) and subgroups of special interest.

4. To explore the performance of **different coding definitions** for COVID-19 and how they influence the size of the cohort

Out of scope:

To assess comparative effectiveness and safety between individual treatments administered for COVID-19 infection or between treated and untreated patients.

To validate definition for COVID-19 using clinical adjudication of individual patient medical records sampled from the study population

[figure not shown]
Section 7.0 Research Methods

[figure not shown]
[figure not shown]
7.1 Study Design

This is a descriptive cohort study using secondary data sources (electronic medical records) from eight databases in seven European countries reflecting either hospital or ambulatory care setting. The study population will be comprised of a cohort of diagCOVID-19 or labCOVID-19 patients in the database within the study time period.

Patients may be either diagnosed and followed-up in an outpatient or in an inpatient setting (according to the database) and they might be new users or prevalent users of systemic glucocorticoids. Based on these 2 characteristics, four mutually exclusive cohorts will be created overall. Not all cohorts can be constructed in each database. They will be used differently depending the objective as mentioned in the analysis section. An overview of the study design is provided in Figure 1 below.

Patients will be followed during the study period from COVID-19 diagnosis date to assess the utilization of systemic glucocorticoids specifically indicated for the treatment of COVID-19 and from treatment index date for the occurrence of outcomes of interest.

[figure not shown]

Figure 1 Study design

7.2 Setting

The proposed setting for this study will be within seven European countries (Belgium [general practice EHR], Netherlands [general practice EHR], Germany [general practice EHR], France [general practice EHR], Italy [general practice EHR], Spain [general practice EHR, hospital EHR], and the United Kingdom [general practice EHR]).

The study will be conducted using data from multiple real-world data (RWD) sources previously mapped to the OMOP CDM in collaboration with the OHDSI and European Health Data and Evidence Network (EHDEN) initiatives.

Each cohort is defined in a separate setting (either hospital or primary care) based on the data source type and will be described at diagnosis of diagCOVID-19 or labCOVID-19 accordingly. The follow up will take place in the same setting and switch of setting (hospitalization for ambulatory cohorts or discharge for hospital cohorts) during follow up will be captured as an outcome.

7.2.1 Study Time Period

The study period, when index events and outcomes of interest can be observed, will start from 1st January 2020 and end at the latest available date for all data sources in 2020 (Table 1) which can be 1st January 2021, at the latest. Before the final extraction and analysis, data will be updated as frequently as possible, in collaboration with local data partners. The results will not be refreshed after the data extraction which will take place on 1st February 2021 at the latest.

Table 1 Data lock point for each available database

Database	Actual/Future data lock points
LPD Belgium	December 2020
LPD France	November 2020
DA Germany	December 2020
UK IMRD	June 2020
LPD Italy	December 2020
IPCI	December 2020
SIDIAP	December 2020
HM Hospitales	April 2020

7.2.2 Patient Selection

7.2.2.1 Inclusion Criteria

Four cohorts will be created based on healthcare setting and type of steroid use. Their eligibility criteria being described below (using Covid-19 catch-all definition Section 7.3.1):

Ambulatory prevalent user

- Have at least 365 days of continuous observation time prior to cohort entry
- Have a glucocorticoid (oral or parenteral) exposure in the 120 days prior to diagnosis date (unrelated to COVID-19 diagnosis)
- Have a positive PCR test for SARS-CoV-2 (labCOVID-19) or a confirmed COVID-19 diagnosis (diagCOVID-19)
- Have no hospitalizations in the 30 days prior to or on index

Ambulatory naive user

- Have at least 365 days of continuous observation time prior to cohort entry
- Have no glucocorticoid (oral or parenteral) exposure in the 120 days prior to index (unrelated to COVID-19 diagnosis)
- Have a positive PCR test for SARS-CoV-2 (labCOVID-19) or a confirmed COVID-19 diagnosis (diagCOVID-19)
- Have no hospitalizations in the 30 days prior to or on index

Hospitalized prevalent user

- Have a glucocorticoid (oral or parenteral) exposure in the 120 days prior to index (unrelated to COVID-19 diagnosis)
- Have a positive PCR test for SARS-CoV-2 (labCOVID-19) or a confirmed COVID-19 diagnosis (diagCOVID-19) (index date)
- Are hospitalized 30 days prior or after diagnosis index date
- Have no intensive services in the 30 days prior to or on index

Hospitalized naïve user

- Have no prior exposures to glucocorticoids in the 120 days prior to index
- Have a positive PCR test for SARS-CoV-2 (labCOVID-19) or a confirmed COVID-19 diagnosis (diagCOVID-19)
- Are hospitalized 30 days prior or after diagnosis index date
- Have no intensive services in the 30 days prior to or on index

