6.2 Primary Objective

To describe utilization of systemic glucocorticoids (e.g., dexamethasone, prednisolone, methylprednisolone or hydrocortisone) for treatment of COVID-19 in two settings: hospitalized (in hospital care) and ambulatory (any care received outside of hospital) within 90 days following COVID-19 diagnosis. The following variables will be described:

- Prevalent use or naïve (incident) use of systemic glucocorticoid at date of diagnosis of COVID-19
- Concomitant use of other medications (number and type) and invasive/non-invasive respiratory support during follow up
- Type of systemic glucocorticoid received
- Time to systemic glucocorticoid initiation from COVID-19 diagnosis
- Route of administration
- Systemic glucocorticoid daily dose at initiation (treatment index date), cumulative duration, distribution of duration of use and cumulative dose of systemic glucocorticoid received
- For prevalent users: proximity of previous glucocorticoid use to COVID-19 diagnosis (current use (concomitant on date of COVID-19 diagnosis, recent use (between 15-30 days before date of COVID-19 diagnosis) or remote use (use ended more than 30 days before date of COVID-19 diagnosis))

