Steroids often have adjusted dose regimens such that drug may be slowly increased or decreased over time and short acute treatment episodes are also possible. Such changes in dose over time will not be examined, however total cumulative dose will be examined in relation to outcomes of interest (see below).

Cumulative dose

For glucocorticoids used in COVID-19 indication, orally administered, if quantity is available, the formula to calculate the cumulative exposure in mg is described below:

$$Cumulative\ dose_{solid}[mg] = \sum_{all\ exposures} quantity \times amount_value [mg]$$

If the **quantity is missing**, the number of units per day for solid formulations are extracted. The cumulative exposure in mg can then be calculated using the following formula:

$$Cumulative\ dose_{solid}[mg] = \sum_{exposures} units\ per\ day \times amount_value [mg] \times duration$$

For intravenous administration (bolus administration), the dose administered each time will be counted.

$$Cumulative\ dose\ intravenous [mg] = \sum_{all\ exposures} amount_value [mg]$$

Exposure groups for incidence calculation (secondary objective 2 and 3)

For the incidence rates calculation, an on-treatment exposure will be considered with mutually exclusive groups to allow calculation of incidence rates.

Each person will be classified as belonging to one of the following mutually exclusive exposure groups at treatment index date following COVID-19 diagnosis:

- Use of systemic glucocorticoids without other treatments for COVID-19 (drug and respiratory support)
- Use of systemic glucocorticoids plus other treatments for COVID-19 (drug and respiratory support)
- Only other treatments and respiratory support with no systemic glucocorticoids

- No specific treatments for COVID-19 infection (other concomitant treatments for indications other than for COVID-19 are allowed)

A single prescription would be enough to consider the patient as exposed. See section 7.3.2.1 for description of 'other treatment for COVID-19' that are included.

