7.3.5 Other Variables

Age – measured both as continuous and categorical variable in years. The following categories will be created:

- <18
- ≥18 and <65
- ≥ 65 and <75
- ≥75

Sex

- Male
- Female

Index month of diagnosis

Comorbidities

- Hypertension
- Type 2 diabetes mellitus
- Chronic obstructive pulmonary disease (COPD)
- Asthma
- Chronic kidney disease
- Ischemic stroke or haemorrhagic stroke
- Heart failure
- Acute myocardial infarction
- Arrhythmia

- Venous thromboembolism (VTE) or pulmonary embolism (PE)
- Obesity (using diagnosis codes)
- Smoker
- Alcohol/Drug abuse
- Autoimmune conditions (type 1 diabetes mellitus, rheumatoid arthritis, psoriasis, psoriatic arthritis, multiple sclerosis, systemic lupus erythematosus, Addisons, Graves, Sjogrens, Hashimoto, myasthenia gravis, autoimmune vasculitis, pernicious anaemia, celiac disease, scleroderma, sarcoid, ulcerative colitis, Crohn disease)
- Organ transplantation,
- Cancer
- Dementia,
- Major psychiatric disorder

These will be used to describe the cohorts at relevant index dates(s) and some of these will be selected as risk factors/confounders for the incidence rates analysis, see section 7.7 for details.

Respiratory support

Patients will be considered having adjunctive respiratory support if available medical records data are available for the following interventions on or post COVID-19 diagnosis:

- Any type of respiratory support
- Invasive mechanical ventilation (including ECMO)
- ECMO only

If no records are observed, then the patient will be considered as receiving no respiratory support.

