SIDIAP is collected from EHR records of patients receiving primary care delivered through Primary Care Teams (PCT), consisting of GPs, nurses and non-clinical staff. The Catalan Health Institute manages 286 out of 370 such PCT with a coverage of 5.6M patients, out of 7.8M people in the Catalan population (74%). The database started to collect data in 2006. The mean follow-up is 10 years. The observation period for a patient can be the start of the database (2006), or when a person is assigned to a Catalan Health Institute primary care centre. Date of exit can be when a person is transferred-out to a primary care centre that does not pertain to the Catalan Health Institute, or date of death, or date of end of follow-up in the database. Drug information is available from prescriptions and from dispensing records in pharmacies. Drugs not prescribed in the GP setting might be underreported; and disease diagnoses made at specialist care settings are not included. Studies using SIDIAP data require previous approval by both a Scientific and an Ethics Committee (9).

Hospital de Madrid (HM) Hospitales (Spain)

Hospital de Madrid (HM) Hospitales data are made available through partnership with SIDIAP. The HM Hospitales database covers in-patient care delivered across a network of private hospitals in Spain. HM Hospitales covers more than 17M patients, out of whom a subset will be catalogued and followed for acute care delivered for suspected COVID-19 onset. This database covers more than 2300 confirmed COVID-19 cases and all in-patient hospital care, including the data of admission, conditions, procedures and medicines dispensed in hospital, date of discharge, and date of known death or date of end of follow-up in the database. Studies using HM Hospitales data require review and approval from data custodians at SIDIAP authorised to execute observational network analyses. The number of newly diagnosed patients in each database per month since the outbreak of COVID-19 can be derived from the databases.

None of the databases, except SIDIAP have linkage between primary and secondary care setting.

A database profiling, describing a range of variables in terms of data quality and completeness, as well as attrition tables for COVID-19 populations can be found at the following link:

https://dqdashboard.iqvia.com/ema_report1/.

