If exposure to glucocorticoids as second or third treatment occurs very often, a large proportion of patients will be censored, leading to limited data to assess the outcomes of interest.

Mitigation – an ITT sensitivity analysis is proposed in case censoring is very large (>70%)

7.9.2 **Databases related limitations**

Linkage between primary and secondary care

Seven out of eight databases will not have linkage between primary and secondary setting, and a consequence of this is that patient follow up time will be fragmented. Especially in the hospital setting, the access to medical history of the patient is limited and the patients who had prior exposure of glucocorticoids in primary care risk to be misclassified as naïve users.

Primary care databases

Severe outcomes that lead to hospitalization are less likely to be captured., although hospitalization is captured in some of the primary care databases.

If patients are free to change general practitioners and they are not tracked across different GPs or if they are treated. In private practice, their exposure will be underestimated and the follow up will be fragmented.

As the hospital and ambulatory settings are not linked, patients who had prior exposure of glucocorticoids in hospitals will be misclassified as naïve users.

Hospital setting databases

As the lookback period in the hospital setting is in general absent or reduced, there will be an under-ascertainment of baseline comorbidities.

Mortality data

The mortality information (vital status) is under-captured in some data sources. Three of them, DA Germany, LPD France and LPD Italy do not record vital status at all. For SIDIAP, the vital status comes from a regional mortality register while for HM Hospitales, the vital status comes directly from hospital records. For IMRD UK and IPCI, the vitals status information comes from GP recording.

Section 8.0 Protection of Human Subjects

For this study, participants from various EU member states will process personal data from individuals which is collected in national/regional electronic health record databases. Due to the sensitive nature of this personal medical data, it is important to be fully aware of ethical and regulatory aspects and to strive to take all reasonable measures to ensure compliance with ethical and regulatory issues on privacy.

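### In six unlinked primary-care databases, unrecorded respiratory support is counted as none, and the ambulatory entry rule cannot exclude admissions that are not captured

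*Protocol*

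**What the plan says.** **Respiratory support.** Section 7.3.5 settles the absence of a record outright: "If no records are observed, then the patient will be considered as receiving no respiratory support". The rule is not limited to any database or cohort. Section 6.2 lists among the variables of the primary objective "Concomitant use of other medications (number and type) and invasive/non-invasive respiratory support during follow up". Sections 7.3.2.3 and 7.7.4 use respiratory support again, together with other drugs, to separate four mutually exclusive exposure groups for secondary objectives 2 and 3: glucocorticoids alone, glucocorticoids plus other treatment, other treatment only, and no specific treatment.

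**Entry to the ambulatory cohorts.** Section 7.2.2.1 requires for both of them: "Have no hospitalizations in the 30 days prior to or on index". It has no provision for a database that does not see admissions. Section 7.2 adds: "Each cohort is defined in a separate setting (either hospital or primary care) based on the data source type".

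**What the databases can see.** Section 7.4 states: "None of the databases, except SIDIAP have linkage between primary and secondary care setting". Section 7.9.2 agrees ("Seven out of eight databases will not have linkage between primary and secondary setting") and says that severe outcomes leading to admission are less likely to be captured in primary care, "although hospitalization is captured in some of the primary care databases". Those databases are not named there, and the completeness of capture is not given.

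**The concern.** For both variables, a source that cannot fully observe hospital care is used as if a missing record meant that nothing happened. For respiratory support this is written down as a rule. For admissions it follows from how a record-based exclusion works.

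Two results are at stake. First, respiratory support is described by setting under the primary objective, and a low percentage in a primary-care database would reflect what the source records as much as what patients received. Second, the exposure groups depend on it. A glucocorticoid patient whose only other treatment was support given in hospital is classed as glucocorticoids alone. A patient without glucocorticoids whose only treatment was such support is classed as having no specific treatment. The incidence rates in those groups would then include patients with more severe disease than the labels say.

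For entry, setting is the main axis of the study. Section 7.9.1 says that PCR results are available only in SIDIAP, so in the unlinked primary-care databases the index date rests on a diagnosis code. If that code is entered after a hospital stay that the database does not hold, the patient passes the entry criterion.

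**Working it through.** **1. Linkage count.** There are eight databases and one is linked (SIDIAP): 8 − 1 = 7, which reproduces the figure in section 7.9.2. One of the seven is the hospital source, HM Hospitales: 7 − 1 = 6 unlinked databases out of the seven in primary care.

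**2. Effect on respiratory support.** Let r be the true share of patients with support and s the probability that it is recorded. The recorded share is r × s. The share of the no-support class that truly had support is r(1 − s)/(1 − r·s). Neither r nor s is in the protocol. For an assumed r = 10%:

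| s | Recorded share | Share of the no-support class that had support |
|---|---|---|
| 0 | 0% | 10.0% |
| 0.1 | 1.0% | 0.09/0.99 = 9.1% |
| 0.25 | 2.5% | 0.075/0.975 = 7.7% |
| 0.5 | 5.0% | 0.05/0.95 = 5.3% |
| 0.9 | 9.0% | 0.01/0.91 = 1.1% |

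Not every patient with missed support changes exposure group. Someone with another Appendix 3 drug recorded as COVID-19 treatment stays in the same group. The movement comes from patients whose only other treatment was the unrecorded support.

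**3. Effect on ambulatory entry.** Let h be the true share admitted in the 30 days before or on index, and s the probability that the admission is recorded. The wrongly included share of the cohort is h(1 − s)/(1 − h·s). Both inputs are assumed. The upper h values borrow the 10–20% progression to pneumonia and ARDS in section 5.0, only to set a range:

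| h | s = 0 | s = 0.5 | s = 0.9 |
|---|---|---|---|
| 2% | 2.0% | 1.0% | 0.2% |
| 5% | 5.0% | 2.6% | 0.5% |
| 10% | 10.0% | 5.3% | 1.1% |
| 20% | 20.0% | 11.1% | 2.4% |

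With full capture (s = 1) the share is 0. Admissions after index do not count here, because section 7.3.4 treats them as an outcome of the ambulatory cohorts.

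**4. How many patients are in unlinked primary care.** Section 7.5 gives 153,759 patients in total, about 2,000 of them in hospital data, and a range per database of 1,417 to 124,221. It does not say which database is the largest.
- If SIDIAP is the largest: (153,759 − 124,221 − 2,000)/(153,759 − 2,000) = 27,538/151,759 = 18.1% of non-hospital patients are in unlinked data.
- If SIDIAP is the smallest: (151,759 − 1,417)/151,759 = 99.1%.

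Section 7.7 presents results separately for each database, so a large SIDIAP would not dilute the error in the others.

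**5. Limitations section.** Section 7.9.2 covers fragmented follow-up, under-captured severe outcomes, earlier glucocorticoid users misclassified as naive, and missing comorbidities. It does not mention setting misclassified at entry or unobserved support counted as none.

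**The case against.** The protocol is open about the missing linkage, says that some primary-care databases do capture admissions, includes a linked database, rules out comparative analysis and reports each database separately. The entry criterion is an ordinary record-based exclusion, and nowhere does the text say that an unrecorded admission did not occur. Nor do the documents show how often a GP codes COVID-19 after a discharge. These points stand. They limit how far the entry problem can be asserted: it is possible, uneven across databases and unmeasured. They do not answer the respiratory-support rule, which is explicit and universal.

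A reader might infer three stronger points that the documents do not support.

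- *Ambulatory respiratory support is zero by construction.* Appendix 1 lists oxygen therapy (6.1) and a home visit for ventilation care (6.2), both recordable outside hospital. The table in the working shows zero only at s = 0. Under-recording to an unknown degree is as far as the text goes.
- *Ambulatory glucocorticoid use is inflated by hospital-started courses by a stated amount.* Section 6.2 defines ambulatory care as any care outside hospital, so a GP prescription after discharge falls within it, although its start date and severity context may mislead. Assuming 3% true use, 2–10% hospital-managed cases and 15–30% of those with a visible course gives 0.98 × 3% + 0.02 × 15% = 3.24% up to 0.90 × 3% + 0.10 × 30% = 5.7%. None of the three inputs is in the protocol, so this range is no evidence of size.
- *The unlinked databases should be dropped from the ambulatory results.* That could remove up to six databases for a misclassification of unknown size. It is a trade-off and does not follow from the text.

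**Conclusion.** The point holds in two parts of unequal strength.

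For respiratory support, following section 7.3.5 as written gives a wrong result wherever support given in hospital is not visible. The recorded share is biased downwards, unobserved support is reported as none, and some patients move from glucocorticoids plus other treatment to glucocorticoids alone, or into the group with no specific treatment. This rests on the protocol's own rule and its own account of linkage.

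For ambulatory entry, section 7.2.2.1 can exclude only recorded admissions, so where they are not captured some patients hospitalised before or on index can enter. This is implied by the criterion and is an omission from section 7.9.2.

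No single size can be given for either part. At an assumed true share of 10%, the misclassified fraction runs from 10.0% with no capture to 1.1% with 90% capture. It will differ between databases.

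**What to change.** 1. Amend section 7.3.5 so that, in databases without hospital capture, respiratory support is reported as not captured instead of no. In sections 7.3.2.3 and 7.7.4, define the exposure groups in those databases on drugs only, and flag the results as not directly comparable with databases that observe respiratory support. The flag should carry into section 7.7.7, where estimates by treatment group may be pooled.
2. State for each database whether inpatient admissions are observable. Where they are not, keep the ambulatory results in the report with a footnote that prior hospitalisation is not verifiable.
3. In SIDIAP, run the entry criterion of section 7.2.2.1 with and without the linked hospital records, and report cohort size and glucocorticoid use both ways. This gauges the misclassification in SIDIAP; applying it to other databases remains an assumption.
4. Add setting misclassification at entry to section 7.9.2.

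The cost is one extra cohort run, some protocol wording, and exposure groups that are less uniform across databases. No database is lost.

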7.3.2.1 Glucocorticoids

Glucocorticoids used in COVID-19 indication

The primary treatment group of interest is based on exposure to systemic glucocorticoids. The following drugs will be considered as being used for COVID-19 diagnosis:

- Dexamethasone (H02AB02)
- Prednisone (H02AB07)
- Prednisolone (H02AB06)
- Methylprednisolone (H02AB04)
- Hydrocortisone (H02AB09)

Only glucocorticoids which were investigated in clinical trials (13,21) or are recommended by clinical guidelines are included (22–24) to avoid misclassification of steroids used for other conditions. As indication is not captured in the available databases, a glucocorticoid treatment will be considered to have been initiated for COVID-19 treatment if:

For incident users

- The glucocorticoid treatment was initiated between 2 before and 30 days after COVID-19 diagnosis date (21)
- It is one of the five glucocorticoids recommended for COVID-19 as above

For prevalent users

- The glucocorticoid treatment was initiated between 2 before and 30 days after COVID-19 diagnosis date
- It is one of the five glucocorticoids recommended for COVID-19 as above
- The glucocorticoid started after COVID-19 diagnosis differs from the chronically used glucocorticoids OR there is a change in dose or schedule of administration compared to the prevalent use, occurred after COVID-19 diagnosis.

Glucocorticoids for pre-existing conditions

For the prevalent users, any steroid in the ATC class H02 glucocorticoids for systemic use will be considered. A patient is defined as a systemic glucocorticoids prevalent user if it has at least one prior exposure to systemic² glucocorticoids in the 120 days prior to diagnosis index date.

For the description of prevalent users of glucocorticoids, categories of use will be created based on proportion of days covered (PDC) during the lookback period. PDC is calculated as the number of days in period covered by prescriptions divided by number of days in the period.

- PDC > 85% as heavy user
- PDC 50-85% as moderate user
- less than 50% PDC as light user

Another categorization of prevalent glucocorticoids user will be based on how recently in the past the last prescription was observed:

- current use (concomitant on date of COVID-19 diagnosis)
- recent use (between 15-30 days before date of COVID-19 diagnosis)
- remote use (use ended more than 30 days before date of COVID-19 diagnosis)

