7.5 Sample Size

Based on database characterization conducted prior to this protocol, the eight databases mentioned above include between 1,417 to 124,221 diagCOVID-19 and labCOVID-19 patients per database, and a total of 153,759 patients, only one database observing hospitalized patients (around 2,000 patients).

The number of patients in each of the proposed EU countries is projected to be modest, but it is difficult to confirm and likely to vary between data sources. As the primary objective is a descriptive one, the aim is to observe a sufficient number of patients in order to estimate the frequency of drug utilization measures with an acceptable level of precision. The 95% CI width will provide an indication of precisions of the point estimate; the upper and lower limit will provide a range of credible values consistent with observed data.

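### In the only hospital database the naive/prevalent split cannot separate home glucocorticoid users from non-users, and home users filed as naive can enter the analysis as COVID-19 treatment starts

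*Protocol*

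**What the plan says.** Section 7.2.2.1 creates four cohorts by setting and user type. The hospital prevalent cohort requires "Have a glucocorticoid (oral or parenteral) exposure in the 120 days prior to index (unrelated to COVID-19 diagnosis". The hospital naive cohort requires "Have no prior exposures to glucocorticoids in the 120 days prior to index". Both ambulatory cohorts need at least 365 days of prior observation; the hospital cohorts have no such requirement, and 7.2.3 applies the 365-day history window to outpatients only.

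Section 7.5 says there is "only one database observing hospitalized patients (around 2,000 patients". Section 7.4 describes this source: "The HM Hospitales database covers in-patient care delivered across a network of private hospitals in Spain". Its listed contents include "procedures and medicines dispensed in hospital, date of discharge", with no outpatient prescriptions. On linkage, 7.4 states: "None of the databases, except SIDIAP have linkage between primary and secondary care setting". Section 7.9.2 adds, under hospital databases, "As the lookback period in the hospital setting is in general absent or reduced", and accepts that patients treated in primary care may be wrongly classed as naive. It gives no mitigation.

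Section 7.3.2.1 says indication is not captured and infers COVID-19 use from drug and timing. For incident users, one of five listed drugs must be initiated between 2 days before and 30 days after diagnosis. Prevalent users must also pass a further test: "The glucocorticoid started after COVID-19 diagnosis differs from the chronically used glucocorticoids OR there is a change in dose or schedule of administration".

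**The concern.** In HM Hospitales the absence of a glucocorticoid record in the prior 120 days does not show absence of use. A patient taking prednisolone at home, with no earlier HM stay, looks the same as one who has never taken a glucocorticoid.

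The classification also decides which treatment rule applies. The test that tells continued therapy from new therapy is reserved for prevalent users. A home user filed as naive does not face it, so the first in-hospital record of a continued drug can be read as the start of COVID-19 treatment.

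That start feeds the hospital half of the primary objective (time to initiation, starting dose, duration and cumulative dose). It also sets the treatment index date from which adverse events and disease outcomes are counted under secondary objectives 2 and 3. The descriptors planned for prevalent users (proportion of days covered; current, recent or remote use) need a prescription history that this source does not hold.

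**Working it through.** The protocol gives no calculation to reproduce here. The figure of about 2,000 in 7.5 is a count from database profiling. The check has two parts.

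**Tracing the rules**

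1. Where can hospital cohorts come from? Section 7.2 assigns setting by type of data source, and 7.5 names one hospital source. SIDIAP is the only linked database, but the abstract lists it under ambulatory care. As written, the hospital split rests on HM Hospitales alone.
2. What can show prior exposure there? Only dispensing in an earlier HM admission, or before the index date within the current one (7.2.2.1 allows admission in the 30 days before diagnosis). Home prescriptions cannot appear.
3. Which treatment rule follows? With no record the patient is filed as naive, and only the drug list and the time window apply. With a record the patient is filed as prevalent, and the change test applies as well.
4. Does 7.9.2 follow this through? It names the misfiling but not its effect on treatment starts. None of the sensitivity analyses in 7.7.8 addresses it.

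**Illustrating the size**

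The only input from the document is N = 2,000 (7.5). The others are assumptions:

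- c, the share of hospital patients on home systemic glucocorticoids: 2%, 5% or 10%
- f, the true rate of new use among the rest: 10%, 30% or 50%
- every home user takes one of the five drugs, continues it in hospital, has the first record in the window and has no earlier HM record

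The formulas are:

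- Home users filed as naive = N × c: 2,000 × 0.02 = 40; 2,000 × 0.05 = 100; 2,000 × 0.10 = 200.
- Share of apparent naive starts that are continuations = c / [c + f(1 − c)].
- Apparent start rate = c + f(1 − c).

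| f | c = 2% | c = 5% | c = 10% |
|---|---|---|---|
| 10% | 0.02/0.118 = 17% | 0.05/0.145 = 34% | 0.10/0.190 = 53% |
| 30% | 0.02/0.314 = 6% | 0.05/0.335 = 15% | 0.10/0.370 = 27% |
| 50% | 0.02/0.510 = 4% | 0.05/0.525 = 10% | 0.10/0.550 = 18% |

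For one intermediate case, c = 5% and f = 20%, there are 100 continuations and 1,900 × 0.20 = 380 true starts. Continuations are 100/480 = 21% of starts, and the apparent rate is 480/2,000 = 24% against a true 20%. The 95% CI half-width for 20% of 2,000 is 1.96 × √(0.2 × 0.8/2,000) = 1.8 points, so the 4-point shift is larger than the interval that 7.5 relies on to convey precision.

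If a quarter of home users did have an earlier HM record, the same case gives 75 continuations among 75 + 380 = 455 apparent starts (16%), an apparent rate of 455/1,975 = 23%, and a prevalent cohort of 25 patients.

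**The case against.** The strongest reply is that the protocol is candid. Section 7.9.2 states the misclassification and the missing look-back, and 7.1 warns that not every cohort can be built in every database. The study is descriptive, reports each database separately, and rules comparative questions out of scope in 6.3. HM Hospitales supplies about 2,000 of 153,759 patients. All of this stands, and it lowers the severity. It does not answer the second step, from misfiling to false treatment starts, which the protocol does not discuss. Hospital care is also one of the two settings in the primary objective.

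Three stronger readings are tempting, and the documents do not support them:

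- **That the hospital cohorts cannot be formed.** They can be, from in-hospital records. What they cannot do is represent home use, and the prevalent cohort is likely to be small and selected.
- **That a naive-versus-prevalent contrast is spoiled throughout.** No such contrast is planned. User type is a descriptive stratum, secondary objective 1 applies it to only some characteristics, and secondary objective 4 does not use it.
- **That every home user becomes a false start.** Systemic glucocorticoids outside the five listed drugs do not qualify. A drug first recorded before the window opens does not qualify either, and that earlier record can move the patient to the prevalent group. The percentages are therefore upper bounds for their assumed inputs.

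Section 7.9.1 also notes that hospital glucocorticoids may be recorded only as ward stock. That lowers recorded use, so the net direction of error in the hospital utilization rate is unknown.

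**Conclusion.** The point holds. In HM Hospitales the 120-day criterion sorts patients by recorded in-hospital exposure, which does not tell home users from non-users. Because the change test depends on that sorting, continued home therapy can be counted as COVID-19 treatment initiation. The first step is disclosed without mitigation; the second is not disclosed.

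The mechanism follows from the text alone. The size does not: the documents give neither the prevalence of home use nor the rate of true new use. Over the assumed ranges, at most about 4% to 53% of apparent naive starts would be continuations. The top of that range pairs the highest assumed home use with the lowest assumed new use. Severity: should be fixed.

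**What to change.** For HM Hospitales, in 7.2.2.1 and 7.7.2 to 7.7.4:

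- Report one hospital cohort. Do not present naive/prevalent as user type. If strata are wanted, label them *prior in-hospital exposure recorded* and *not recorded*.
- Keep the change test of 7.3.2.1 for patients with recorded prior exposure, so that merging the cohorts does not loosen the rule for them.
- Call the treatment variable *in-hospital glucocorticoid use*, and state in 7.7.2 to 7.7.4 and 7.9.2 that continued home therapy cannot be excluded from hospital starts.
- Add a sensitivity analysis on those starts, for example excluding those first recorded on the admission date. It will also remove some genuine starts, so it shows sensitivity and does not give a corrected estimate.
- Limit user type, proportion of days covered and current/recent/remote use to databases with an observable 120-day prescription look-back.

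Relabelling alone leaves continued home therapy in the treated group, which is why the explicit statement and the sensitivity analysis are needed. The cost is protocol wording, one extra analysis and the loss of a hospital user-type breakdown, which this source could not validly supply.
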